5.9.6. Reporting of Deaths

The death of any subject during the study, regardless of the cause, must be reported within 24 hours of the Investigator or the study site personnel becoming aware of the occurrence.

Death cases are to be captured in the SAE and Mortality pages of the eCRF. If an autopsy is performed, the report must also be provided.

Depending on country specific requirements, death cases will be submitted to the appropriate Regulatory Authorities, as well as IEC/IRB(s), as applicable.

5.9.7. Procedure in Case of Pregnancy

If a subject becomes pregnant at any time during the trial, the subject must be withdrawn from the trial and Safety Follow-up procedures should be completed. The Investigator should report the pregnancy to ProductLife Pharmacovigilance within 24 hours of becoming aware of event.

The subject should be followed by the Investigator until completion of the pregnancy. If the pregnancy ends for any reason before the anticipated date, the Investigator should notify ProductLife Pharmacovigilance.

At the completion of the pregnancy, the Investigator will document the outcome of the pregnancy. If the outcome of the pregnancy meets the criteria for immediate classification as an SAE (i.e., postpartum complication, spontaneous abortion, stillbirth, neonatal death, or congenital anomaly), the Investigator should follow the procedures for notification of SAEs.

6. TERMINATION OF THE CLINICAL STUDY

The Sponsor reserves the right to discontinue the study for safety, ethical or administrative reasons.

Any concerned regulatory authorities also have the authority to discontinue this trial.

All Investigators will be notified in writing, outlining the reasons for the discontinuation of the study at their site. Instructions will be provided if assessments beyond the regular per protocol procedures should be necessary.

If a study is prematurely terminated, the Sponsor will promptly inform the IEC/IRB and competent authorities of the termination and its reason(s).

7. STATISTICAL METHODOLOGY

7.1. Sample Size

The primary objective of the study is to evaluate the efficacy of the study drug by the frequency of subjects with overall disease control (including SD, PR, and CR).

The null hypothesis assumes an historical disease control rate of <5%, given that these subjects have already failed progestin therapy. A clinically significant difference is predefined as a 15% increase (i.e. disease control rate of 20%). Using the Fleming's single stage procedure (in which a predetermined number of patients is recruited to the study and a decision about activity is obtained from the number of responses (including SD, PR, or CR) amongst these patients) with the probabilities of type I and type II errors of 5% (one-sided) and 10%, respectively, approximately 40 subjects are planned to be enrolled to Treatment Period 2. It is estimated that approximately 20-25% of subjects will be classified as PrR negative and go directly into Treatment Period 2. This group will represent 14-16 of the Treatment Period 2 subjects. The rate of subjects who will have progressive disease following treatment with megestrol acetate in Treatment Period 1 and then move on to Treatment Period 2 is estimated at 55-60%. These subjects will represent 30-32 of the Treatment Period 2 subjects (estimating that approximately 24-25 subjects treated in Treatment Period 1 will not exhibit progressive disease and will not move into Treatment Period 2.) Estimating the rate of subjects who will be unavailable for disease assessment for various reasons at 10-15%, it is planned to enroll 72 total subjects. An estimated 20% screen failure rate will require up to 90 screened patients to allow for enrollment of 72 subjects.

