1.4 Rationale for Study

Patients with recurrent or persistent endometrial cancer have limited treatment options. Although treatment with progestins provides some benefit and is routinely used to treat patients with PrR-positive recurrent or persistent tumors, only 25% of patients develop a response to these therapies, leaving a majority of the patients with few other options for treatment. Additionally, patients whose tumors do not express PrR are rarely treated with hormonal therapy as the response rate for these treatments in PrR-negative tumors is very low. As such, hormone resistant recurrent or persistent endometrial cancer represents a patient population for which new treatment options are greatly needed. Sodium Cridanimod has been shown to increase endometrial cancer expression of PrR and increase the efficacy of progestin therapy in at least a subset of these patients, which we believe provides a strong rationale for the combination of these agents for the treatment of recurrent or persistent endometrial cancer that has failed hormonal therapy. Additionally, combining progestin therapy with other agents known to increase tumor PrR expression (such as tamoxifen) has shown some success in other studies, supporting the rationale for this study^{11,12}.

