1.5. Rationale for Study Population, Exclusion Criteria

This study will enroll patients with endometrioid histology of the tumor as endometrioid tumors have been shown to be the most sensitive to treatment with hormonal therapy. Additionally, the majority of the tumors previously treated with Sodium Cridanimod and progestins were of the endometrioid

histology. The efficacy of the study treatment in patients with other tumor histologies, or mixed histologies, is difficult to predict. For this reason, inclusion of patients with tumors of other histologies or mixed histology is prohibited with the exception of serous carcinoma¹³. Patients with serous carcinoma are eligible to enter this protocol as this histology was included in a prior trial of Sodium Cridanimod and progestin therapy in recurrent or persistent endometrial cancer with PrR negative tumors.

Endometrial cancer patients whose tumors do not express progesterone receptors are not considered candidates for progestin-based therapy. Patients therefore who have been identified as PrR negative from an archived tumor tissue sample will not be treated with progestin monotherapy and will enroll directly into the combination therapy portion of the trial.

As the main elimination route of Sodium Cridanimod is the kidney, patients with significant kidney disease and a diminished glomerular filtration rate (GFR < 50 mL/min) will not be enrolled in the study. eGFR will be monitored during the study for safety reasons. In the event of an observed renal toxicity, the decision to withdraw the treatment should be made by the Investigator.

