2. STUDY OBJECTIVE(S), DESIGN AND ENDPOINTS

2.1. Study Objectives

2.1.1. Primary Objective

To assess the antitumor activity of Sodium Cridanimod in conjunction with progestin therapy as measured by Overall Disease Control Rate (ODCR) in women with recurrent or persistent endometrial carcinoma not amenable to surgical treatment or radiotherapy who have either failed progestin monotherapy or who have been identified as PrR negative.

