Subjects determined to be PrR negative at Screening will not enroll into Treatment Period 1. These subjects will enroll directly into Treatment Period 2.

2.2.2 Treatment Period 2 (Combination Therapy):

All subjects determined to be PrR negative at Screening and those who received at least 4 weeks of progestin monotherapy and who experienced disease progression during Treatment Period 1 will enter Treatment Period 2 of the study (Visit 1, Day 0).

During Treatment Period 2, subjects will receive Sodium Cridanimod (500 mg, 2 times / week, intramuscularly) in combination with continued progestin treatment (megestrol acetate 160 mg p.o. / day).

- For those subjects who participated in Treatment Period 1, there should be no interruption of progestin therapy between Treatment Period 1 and Treatment Period 2.
- Subjects will receive treatment until disease progression as defined according to RECIST 1.1 Criteria, with response assessments performed at 12-week intervals.

- Confirmation of objective responses in Treatment Period 2 will be performed at least 4 weeks after the criteria for response are first met.

2.2.3 Follow-up Period:

Once subjects progress in Treatment Period 2, treatment will be stopped and the subjects will return for the Safety Follow-up Visit four (4) weeks following the last treatment, and then continue to be followed for a 12-month period for overall survival.

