3.5. Exclusion Criteria

1. Mixed histology of the tumor or evidence of tumor histology other than serous carcinoma or endometrioid type of endometrial carcinoma;
2. Concurrent systemic corticosteroid therapy;
3. Concurrent oral contraceptive use / Women of childbearing potential not using highly effective means of contraception;
4. Pregnancy confirmed by pregnancy test / Lactating women (for women of childbearing potential);
5. Prior therapy with hormonal progestin agents;
6. Patients who are candidates for treatment with standard chemotherapy agents (there is no limit to the number of lines of prior chemotherapy);
7. History of blood clot;
8. History of known bleeding disorder (i.e. disseminated intravascular coagulation or clotting factor deficiency);
9. Major surgery within 4 weeks prior to the start of the study;
10. Patients with clinically significant illnesses which, according to the Investigator, could compromise participation in the study;
11. History of other clinically active malignancies within 5 years, except for carcinoma in situ of the cervix, basal cell carcinoma, or squamous carcinoma of the skin.
12. Known hypersensitivity or idiosyncratic reaction to any of the study drugs (Sodium Cridanimod, megestrol acetate, lidocaine) and excipients;
13. Patients with known brain metastases;
14. Patients currently receiving any other investigational agents;
15. Patients currently receiving any other anticancer therapies;
16. Participation in any other clinical study within the last 4 weeks prior to the start of the study;

Waivers to the exclusion criteria will **NOT** be allowed.

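### Does the pooled disease control null of under 5% fail because about a third of the planned Treatment Period 2 subjects have never had a progestin?

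*Protocol*

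**What the plan says.** The primary objective (Protocol 2.1.1) covers women "who have either failed progestin monotherapy or who have been identified as PrR negative". Protocol 7.1 sets a single null for all of them: "The null hypothesis assumes an historical disease control rate of <5%, given that these subjects have already failed progestin therapy". SAP 6 repeats the reason almost word for word. The synopsis states the same null without a reason.

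The same paragraph of Protocol 7.1 sizes the PrR-negative group: "This group will represent 14-16 of the Treatment Period 2 subjects". It puts the subjects who progressed on megestrol acetate at 30-32. It also allows for losses: "Estimating the rate of subjects who will be unavailable for disease assessment for various reasons at 10-15" per cent.

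On the PrR-negative group, Protocol 2.2 says: "Subjects determined to be PrR negative at Screening will not enroll into Treatment Period 1". Exclusion 5 in Protocol 3.5 bars "Prior therapy with hormonal progestin agents". These women therefore start megestrol acetate and Sodium Cridanimod together.

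The protocol's support for a low rate in this group is qualitative. Section 1.5 says that patients whose tumours lack the receptor "are not considered candidates for progestin-based therapy", and section 1.4 says that "the response rate for these treatments in PrR-negative tumors is very low". The only related number is in Table 5: an 8% objective response rate for PrR below 50 fmol/mg cytosol protein.

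**The concern.** The stated reason for the null is prior progestin failure, and about a third of the planned Period 2 subjects have not failed a progestin. The primary endpoint counts stable disease (Protocol 5.6.3), and no disease control rate of that kind is given for PrR-negative women. The 8% in Table 5 does not help. It uses a different assay and cut-off from the under-1% IHC rule and leaves out stable disease. In a comparable population, disease control could not be lower than objective response.

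If the true null rate in PrR-negative women were well above 5%, the pooled test could reject more often than the stated 5% of the time with no contribution from Sodium Cridanimod. A pooled rate above 5% could then partly reflect first exposure to megestrol. Protocol 7.4.1 shows only the pooled estimate. The RECIST guideline appended to the protocol (its section 4.7.1) asks uncontrolled trials to document the basis for the expected progression-free proportion. That passage concerns PFS and landmark proportions, so it applies to best overall response only by analogy.

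**Working it through.** **Inputs.** Null 5%, alternative 20%, one-sided alpha 5%, power 90%, about 40 subjects; 14-16 PrR-negative and 30-32 progressors; 10-15% not assessable (Protocol 7.1, SAP 6). SAP 6 names the exact single-stage design. Neither document states the number of successes required, so I take the smallest count r that keeps alpha at or below 5%.

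**The plan's own figure.** Alpha = P(X ≥ r) with X ~ Bin(n, 0.05); power = P(X ≥ r) with X ~ Bin(n, 0.20).

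| n | r | alpha | power |
|---|---|---|---|
| 38 | 5 | 4.0% | 90.1% |
| 40 | 5 | 4.8% | 92.4% |
| 41 | 6 | 1.6% | 85.6% |
| 43 | 6 | 1.9% | 88.6% |

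The smallest design meeting both errors is n=38, so about 40 is reproduced. The sizing arithmetic is sound.

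**Share and evaluable numbers.** The extremes are 14/(14+32) = 14/46 = 30% and 16/(16+30) = 16/46 = 35%. Total evaluable: 44 × 0.85 = 37.4 to 48 × 0.90 = 43.2, so 37-43. PrR-negative evaluable: 14 × 0.85 = 11.9 to 16 × 0.90 = 14.4, so m = 12-14.

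**Error when the two routes differ.** The number of successes is Bin(m, q) + Bin(n−m, p), where q is the null rate in PrR-negative women and p the null rate in progressors. Alpha is the probability that this sum reaches r. Neither q nor p is documented. I use q = 8%, borrowed from Table 5 as an illustration only, with three values of p:

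| p (progressors) | n=38-40, r=5 | n=41-43, r=6 |
|---|---|---|
| 5% | 7.3-9.2% | 3.1-4.1% |
| 4% | 4.7-6.2% | 1.8-2.5% |
| 3% | 2.8-3.9% | 0.9-1.3% |

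At n=40 with p = 5% the range is 8.4-9.2%; with p = 3% it is 3.2-3.9%.

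The pooled mean rate largely explains the pattern at n=40. With 13 PrR-negative, (13 × 0.08 + 27 × 0.05)/40 = 6.0%, above the null. With progressors at 3%, (13 × 0.08 + 27 × 0.03)/40 = 4.6%, below it. At n=41-43 the stricter cut-off also leaves room: with p = 5%, alpha reaches 5% only when q is 8.9-10.5%.

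**Higher assumed rates.** With p = 5% and n=40, q = 10% gives 11.5-12.9% and q = 15% gives 21-25%. At n=41-43, q = 15% gives 10-14%.

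**If the rule were instead that the exact two-sided 95% interval excludes 5%.** This needs at least 6 successes at every n from 37 to 43. With q = 8% and p = 5%, alpha is 2.1-4.1% and power 78-89%.

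**What the analysis will use.** SAP 1 says its methods supersede the protocol's. SAP 3.5 plans no formal testing. SAP 4.5 records 25 enrolled. SAP 6 says the sample size calculations no longer apply. SAP 14.4 makes no calculation of disease control. SAP 19 drops the interim analysis. SAP 9.6 already reports efficacy data separately for subjects treated in Period 2 only and for those who came through Period 1.

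**The case for a change.** The strongest case for a change has three parts. First, the sentence is untrue of 30-35% of the planned subjects, and SAP 6 still carries it, so it could pass into the report's design section. Secondly, the tolerance is thin where the design sits: with progressors at 5% and n=38-40, alpha reaches 5% once the PrR-negative rate is 5.2-6.1%. Thirdly, the repair would be cheap: limit the clause to Period 1 progressors, say that the error depends on the PrR-negative rate, and show disease control by entry route.

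The first part stands as a matter of wording. The second stands only on its assumption about progressors. Their rate is undocumented too, and the null is written as under 5%, not as 5%.

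The repair gains little. Saying that the error holds only if the PrR-negative rate is below 5% would be inaccurate: at q = 8% alpha stays below 4% at every n from 37 to 43 when progressors are at 3%. The condition is on the mix of routes, n and the cut-off together. The split by route already exists in SAP 9.6. It would not settle attribution either, because PrR-negative women have no megestrol-only comparator and the primary objective concerns the combination. Even at the planned size the separate intervals would be wide: 2/13 gives an exact 95% interval of 1.9-45.4% and 4/27 gives 4.2-33.7%, against 5.7-29.8% for the pooled 6/40.

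Pooling also has a stated rationale. Protocol 1.4 discusses receptor-positive non-responders and receptor-negative women together, as hormone-resistant disease. That supplies no rate, but it shows that the single null was more than an oversight about who had received a progestin.

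**Conclusion.** No change to the plan follows. The clause about prior progestin failure is a loose justification that fits the progressors and not the PrR-negative, progestin-naive women. The null also has no cited disease control rate behind it for either route. That is a gap in the rationale; it does not show that 5% is the wrong figure or that the stated error fails.

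The direction of any effect depends on two unknown rates. Under the illustrative 8% for PrR-negative women at n=40, alpha runs from 3.2-3.9% (progressors at 3%) to 8.4-9.2% (progressors at 5%); higher assumed rates would inflate it further. These figures rest on an assumed cut-off of at least 5 successes and on 12-14 PrR-negative subjects among those evaluable.

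The decisive point is that nothing now uses this error rate. With 25 enrolled, no test, no disease control rate and the sizing set aside, the effect on reported results is nil. A report author who describes the original design can read the clause as referring to Period 1 progressors and treat the pooled null as an assumption.

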	
quintiles, number of valid cases for continuous variables and n, frequency and percentage for categorical variables with 95% confidence limits, when appropriate).
 
All subjects who received a full or partial dose of the study drug (in Treatment Period 2) on at least one occasion are considered evaluable subjects for safety analysis. All treated subjects in Treatment Period 2 who also undergo a CT or MRI scan with tumor assessment after 12 weeks, or who discontinue treatment prior to 12 weeks solely due to disease progression, will be included in the Full Analysis Set (FAS), which will be used for the efficacy evaluation. The Per Protocol population (all FAS subjects, excluding those for whom major protocol violations have been identified) will be used in the sensitivity analyses for all secondary efficacy endpoints.
 
The ODCR will be determined as the proportion of treated subjects who have achieved SD, PR or CR. The ORR will be determined as the proportion of treated subjects who have achieved CR or PR. Estimates of the ORR and the ODCR will be presented with the corresponding 95% confidence interval. PFS, duration of stable disease, and OS will be analyzed using the Kaplan-Meier method. The Kaplan-Meier survival curves will be plotted. OS is defined as the time from the first dose of study drug (beginning of Treatment Period 2) until the date of death from any cause. Subjects who do not die will be censored for this analysis at the last documented date at which the subject is known to be alive. PFS is defined as the time from the first dose of study drug (beginning of Treatment Period 2) until objective tumor progression or death. Medians for time to event variables will be presented with the corresponding 95% confidence intervals.

Interim Analysis	
Interim analysis will be performed for the primary efficacy endpoint (ODCR) once the first tumor assessment during Treatment Period 2 is completed for at least 20 enrolled subjects. An interim analysis of all efficacy endpoints (with the exclusion of overall survival) may also be performed once all enrolled subjects have entered the Follow-up Period and are being followed for overall survival. Analysis of all safety endpoints will also be included in any interim analyses.

Number of Study Centers (and Locations) Planned	
Up to 50 study sites in the US and Europe are planned for enrollment.

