7.2.2. Full Analysis Set (FAS)

The FAS will consist of all subjects treated in Period 2 who either undergo a CT or MRI scan with tumor assessment at Visit 4 (i.e. they have not discontinued treatment prior to Visit 4) or those who have discontinued Treatment Period 2 prior to Visit 4 solely due to documented disease progression. This population will be used for efficacy evaluation.

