7.4. Analysis of Efficacy

The Full Analysis Set will be used for all efficacy analysis. The Per Protocol Set will be used for supportive analysis of all efficacy parameters.

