4.9. Reporting best response results

4.9.1. Phase II trials

When response is the primary endpoint, and thus all patients must have measurable disease to enter the trial, all patients included in the study must be accounted for in the report of the results, even if there are major protocol treatment deviations or if they are not evaluable. Each patient will be assigned one of the following categories:

1. Complete response
2. Partial response
3. Stable disease
4. Progression
5. Inevaluable for response: specify reasons (for example: early death, malignant disease; early death, toxicity; tumour assessments not repeated/incomplete; other (specify)).

Normally, all eligible patients should be included in the denominator for the calculation of the response rate for phase II trials (in some protocols it will be appropriate to include all treated patients). It is generally preferred that 95% two-sided confidence limits are given for the calculated response rate. Trial conclusions should be based on the response rate for all eligible (or all treated) patients and should not be based on a selected 'evaluable' subset.

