5.3 Dose Modifications

There will be no allowed modifications to the dosage, including dose reduction, of either MA or SC during the trial.

If an injection of SC is not administered on the scheduled dosing date, this can be done during the next two days but no later than 1 day before the next scheduled dose. The subsequent injection of SC should be given in accordance with the study drug administration schedule. If a subject misses a dose of MA, the next dose should be taken at the regularly scheduled time.

SC and MA combination therapy should be discontinued if an AE of Grade 3 or higher (in accordance with NCI-CTCAE [National Cancer Institute-Common Terminology Criteria for Adverse Events] Version 4.03 criteria) is observed and determined to be potentially related to either medication. When combination treatment is discontinued, both SC and MA are to be discontinued. Monotherapy in Treatment Period 2 is not permitted. The treatment will not be re-started and the subject will be withdrawn from Treatment Period 2 and enter the Follow-Up Period.

6. Sample Size and Power Considerations

The primary objective of the study is to evaluate the efficacy of the study drug by the frequency of subjects with overall disease control (CR, PR and SD). The null hypothesis assumes an historical disease control rate of < 5%, given that these subjects have already failed progestin therapy. A clinically significant difference is predefined as a 15% increase (i.e. disease control rate of 20%). Using A'Hern's update of Fleming's single stage procedure (in which a predetermined number of subjects is recruited to the study and a decision about activity is obtained from the number of responses [including CR, PR] and SD amongst these subjects) with the probabilities of type I and type II errors of 5% (one-sided) and 10%, respectively, approximately 40 subjects are needed to contribute to the primary analysis in

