8.2 Full Analysis Set

The Full Analysis Set (FAS) will consist of all Safety Population subjects treated in Treatment Period 2 who either undergo a tumor assessment at Visit 4, Week 12 (i.e. they have not discontinued Treatment Period 2 prior to Visit 4, Week 12) or those who have discontinued Treatment Period 2 prior to Visit 4, Week 12 solely due to documented disease progression since Treatment Period 2 dosing started. This population will be used for efficacy evaluation.

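### SAP efficacy listings 16.2.6.4 to 16.2.6.7 are limited to the Full Analysis Set, although SAP section 14 promises them for every Treatment Period 2 subject; the denominator wording for the abandoned disease control rate is also unreconciled

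*Protocol*

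**What the plan says.** **Outputs still to be produced (SAP).**

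- Section 14 drops the two rates but commits to a per-subject listing of best overall response, duration of stable disease where applicable, PFS and OS for each subject in Treatment Period 2. Sections 14.6 to 14.8 repeat this for duration of stable disease, PFS and OS.
- Section 14.3 and Figure 14.2.1.1 define the swimmer's plot, which shows best overall response, on all Safety Population subjects who took part in Treatment Period 2.
- Section 25 gives the population of listings 16.2.6.4 (best overall response), 16.2.6.5 (duration of stable disease), 16.2.6.6 (PFS) and 16.2.6.7 (OS) as the FAS.
- Section 8.2 builds the FAS from subjects with a Visit 4 (Week 12) tumor assessment plus "those who have discontinued Treatment Period 2 prior to Visit 4, Week 12 solely due to documented disease progression". Protocol 7.2.2 has the same limit: "those who have discontinued Treatment Period 2 prior to Visit 4 solely due to documented disease progression".

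**Design text on the disease control rate (ODCR), no longer calculated.**

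- Protocol 7.1: "a decision about activity is obtained from the number of responses (including SD, PR, or CR) amongst these patients", with "approximately 40 subjects are planned to be enrolled to Treatment Period 2".
- Protocol 7.4: "The Full Analysis Set will be used for all efficacy analysis".
- Protocol synopsis, Statistics: "The ODCR will be determined as the proportion of treated subjects who have achieved SD, PR or CR".
- SAP section 6 rewords the 40: "approximately 40 subjects are needed to contribute to the primary analysis in" Treatment Period 2. It names A'Hern's update of Fleming's procedure.
- SAP 14.4 takes the ODCR relative to an efficacy population, a term that SAP section 8 does not define.
- SAP 14.5 counts subjects with no on-study assessment for safety reasons as non-responders for ORR.

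**The concern.** With ODCR and ORR dropped, listing 16.2.6.4 is where a reader of the study report would count disease control, and listings 16.2.6.6 and 16.2.6.7 are where the reader would look for progression and death. If these listings hold only FAS subjects, they leave out the people who stopped before Week 12 because of toxicity, death without documented progression, or closure of the study. Section 14 says they will be there, and the swimmer's plot will show them. The same report would therefore present best overall response on two different sets, and the listings would hold the more selected one.

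For the design record, a count-based decision needs one denominator. The synopsis, SAP 14.4 and SAP 14.5 do not agree with the FAS named in Protocol 7.2.2 and 7.4 and SAP 8.2. Had the ODCR been analysed, the choice could have decided a borderline result.

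**Working it through.** **1. Who is missing from the listings.** Apply the SAP's own definitions to a subject treated in Treatment Period 2 who leaves before Visit 4.

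| Subject | In FAS (8.2)? | Status under 14.3, 14.7, 14.8 | Swimmer's plot | Listings 16.2.6.4, .6, .7 |
|---|---|---|---|---|
| Stops solely for documented progression | Yes | Progression; PFS event | Yes | Yes |
| Dies, progression not documented | No | PFS event and OS event (death from any cause) | Yes | No |
| Stops for toxicity | No | Usually NE; PFS censored; OS followed | Yes | No |
| Stops because the study closes | No | Usually NE; PFS censored; OS censored at last contact if alive | Yes | No |

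The second row matters most: the SAP defines the death as an event for both endpoints, and the event listings omit it. Listing 16.2.6.5 is affected less, because duration of stable disease exists only if best overall response is SD. A subject with an unscheduled scan showing SD at 6 weeks or later (the minimum in SAP 14.2) who then stops for toxicity would still be lost from it.

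**2. How many.** The documents do not say how many of the 25 enrolled (SAP 4.5) reached Treatment Period 2. If the planning fractions held (assumption):

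- Planned entrants: 14 + 30 = 44 to 16 + 32 = 48, out of 72.
- Scaled to 25: 25 × 44/72 = 15.3 to 25 × 48/72 = 16.7.
- 10-15% not assessable: 0.10 × 15.3 = 1.5 to 0.15 × 16.7 = 2.5, so about 2.

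Early closure could raise this. For illustration only, take 16 entrants, 2 of them excluded, and 3 with disease control: 3/14 = 21.4% from the listing against 3/16 = 18.8% of those treated.

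**3. Design record: the plan's figure.** Inputs from Protocol 7.1 and SAP section 6: null rate 5%, alternative 20%, one-sided type I error 5%, type II error 10%. For X ~ Binomial(n, p), alpha = P(X ≥ r | 0.05) and power = P(X ≥ r | 0.20).

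- The smallest n meeting both limits is 38 with r = 5: alpha 0.0397, power 0.9014.
- At n = 40, r = 5: alpha 0.0480, power 0.9241. At r = 4 alpha is 0.138; at r = 6 power is 0.839.

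So about 40 reproduces. The entrants less the allowance run from 44 × 0.85 = 37.4 to 48 × 0.90 = 43.2. The 40 therefore fits an assessable count (SAP wording) better than an enrolled count (protocol wording).

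**4. Design record: does the denominator matter?** The smallest r with exact alpha at or below 5% is 5 for n = 29-40 and 6 for n = 41-53. Take 46 treated, 40 assessable and 5 with control:

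- FAS, n = 40: P(X ≥ 5 | 0.05) = 0.048, a pass.
- All treated, n = 46: P(X ≥ 5 | 0.05) = 0.079, a fail (6 needed).

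At a FAS of 41-43 (48 treated or fewer), both sets need 6 and agree.

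**The case against.** **The listing gap is small and the information is elsewhere.** The swimmer's plot shows every treated Treatment Period 2 subject, listing 16.2.3 gives reasons for exclusion from each set, and listing 16.2.7.7 gives deaths on the Safety Population. Many excluded subjects would be NE in any case. SAP 14.8 also names the FAS, with the Per Protocol Set, for Kaplan-Meier work, so a FAS label is not out of place. All this is true, and nothing is concealed. It does not remove the contradiction: sections 14 and 14.6 to 14.8 promise the data for Treatment Period 2 subjects, and a reader of the PFS and OS listings should not have to recover events from a figure and a safety listing.

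**The design point concerns a decision that no longer exists.** SAP section 1 supersedes the protocol's methods, 3.5 plans no formal testing, section 6 calls the sample size calculations no longer applicable, and 14.4 and 14.5 cancel both rates. This stands in full.

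**The FAS is the designated set and the cut-off is fixed.** Protocol 7.2.2 and 7.4 and SAP 8.2 assign efficacy to the FAS, the synopsis does so shortly before its sentence about treated subjects, and the efficacy population of SAP 14.4 most naturally means the FAS. The Protocol 7.1 phrase describes Fleming's procedure in general. A'Hern's exact method, with the stated error rates, determines the cut-off at any n. This also stands: the unprinted integer is missing detail, not a missing rule.

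**All treated as denominator.** A reader might infer that the design should have used all treated subjects, since the appended RECIST guideline (4.9.1) says "Trial conclusions should be based on the response rate for all eligible (or all treated) patients". That text is written for trials with response as the primary endpoint. SAP 14.5 covers only ORR and only safety-related non-assessment. The rule also has a price: if the 20% applies to assessable subjects and the rest count as not controlled, a cut-off of 6 gives power of 80.0-88.5% at 38-43 assessable, below the planned 90%.

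**Conclusion.** The point holds for the SAP listings. Listings 16.2.6.4 to 16.2.6.7 contradict section 14 and do not match the swimmer's plot. Early deaths without documented progression are PFS and OS events that the PFS and OS listings leave out, and early stops for toxicity or closure are left out as well. The listings would tend to look more favorable than the data. The direction is certain for early deaths and likely for the rest; an excluded subject with an off-schedule SD scan would work the other way. The number affected is unknown, and about 2 rests wholly on the planning fractions.

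The denominator wording is a secondary matter of record. The texts disagree, and a case of 5 controls in 40 assessable of 46 treated shows that it could have mattered. A reader might infer that the trial's reported conclusion, its type I error or its power is compromised. The documents do not support that: no rate, test or decision remains in the SAP. Nor do they support saying that no decision rule existed, since the exact method in SAP section 6 supplies one.

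**What to change.** **SAP section 25:** change the population of listings 16.2.6.4 to 16.2.6.7 to all subjects treated in Treatment Period 2 (16.2.6.5 where duration of stable disease applies), and add a column flagging FAS membership. This matches section 14 and the swimmer's plot, and a reader who wants the FAS can still select it. Cost: four population labels, one flag column and minor programming; no new data.

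**Design record:** in the SAP or the study report, state one set for the ODCR and ORR definitions. The least change is to keep the FAS, read the efficacy population of SAP 14.4 as the FAS, note that the synopsis wording on treated subjects is to be read the same way, and remove the non-responder sentence from SAP 14.5 or say how it fits with SAP 8.2. The exact cut-offs (5 for n = 29-40, 6 for n = 41-53) can be noted there if the design is reused. Cost: two or three sentences. No protocol amendment and no move to an all-treated rule is needed; in a closing study neither would change an output.
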